## 2.3 Target Hb Ranges

In several places, this SAP refers to the following target Hb ranges as specified in the 2 protocols:

- US target: 10-11 g/dL
- EU, ROW target: 10-12 g/dL

## 2.4 Primary Objectives of the Trials

The primary objectives of CI-0014 trial are to compare the efficacy and safety of vadadustat to darbepoetin alfa for the correction and maintenance of Hb in subjects with anemia secondary to NDD-CKD. For CI-0015, the primary objectives relate to the conversion and maintenance of Hb.

## 2.5 Blinding

Both trials are randomized open-label studies. Because of their open-label design, the protocols include careful steps to avoid bias.

An interactive web response (IWR) system governs treatment assignment. The investigators are not aware of which treatment will be assigned next. Because Hb values are objective and will be measured at a central laboratory for all efficacy endpoints, efficacy assessments are not subject to bias.

The studies include blinded adjudication of MACE, the use of an unblinded Independent Data Monitoring Committee (IDMC), and an identical schedule of visits, procedures, and assessments for both treatment groups as strategies to reduce the potential for bias.

To reduce subjectivity of dose adjustment, adjustments to doses for vadadustat and darbepoetin alfa are based on Hb concentration and Dose Adjustment Algorithms. The protocols contain details of the algorithms for vadadustat and darbepoetin alfa.

In order to reduce potential execution bias further, special steps will be taken to restrict access to the study data; the Blinding Procedures and Oversight Plan contains details.

## 2.6 Sample Size

The planned sample sizes are approximately 925 subjects per arm for both Study CI-0014 and Study CI-0015. The sample sizes have been selected to contribute adequate MACE for a pooled analysis that will take place using the results from both studies. See Sections 2.7 and 2.8 for the operating characteristics of the studies, given these samples sizes, with respect to the stand-alone efficacy analysis to be performed on change in Hb and the pooled MACE analysis.

## 2.7 Efficacy

For clarity, this SAP uses the word “mean” to refer to averages over the study groups and “average” to refer to the within-person average during specified evaluation periods.

The primary efficacy endpoint in each study is the change in Hb from Baseline to the average Hb over the PEP (Weeks 24 to 36). Vadadustat and darbepoetin alpha will be compared with respect to the mean change in Hb in each study arm. The primary efficacy objective is to show that vadadustat is noninferior to darbepoetin alfa where establishment of noninferiority is based on a margin of -0.75 g/dL applied to the difference in mean change: vadadustat minus darbepoetin alfa. [Appendix A](#) provides a rationale for this margin.

For the primary efficacy analysis power, the mean change from Baseline in Hb for vadadustat and darbepoetin alfa is assumed to be identical with a common standard deviation (SD) of 1.5 g/dL. For each trial, noninferiority will be established if the lower limit of the 2-sided 95% confidence interval for the difference between the mean in the vadadustat group and the mean in the darbepoetin alfa group is -0.75 g/dL or higher. Under these assumptions, a sample size of 925 subjects per treatment group in the CI-0014 trial will yield greater than 90% power to show

Statistical Analysis Plan AKB-6548-CI-0014 and AKB-6548-CI-0015

noninferiority. The power for the CI-0015 trial is also greater than 90% because the sample size is also planned to be about 925 subjects per group.

If the lower limit of the 2-sided 95% confidence interval for the difference between the mean in the vadadustat group and the mean in the darbepoetin alfa group is above zero, superiority will have been established and the finding will be interpreted as providing evidence of a greater change from baseline in Hb for vadadustat relative to the control arm.

## 2.8 Safety

The primary safety endpoint is the time from the first dose date to the first adjudicated MACE (defined as all-cause mortality, nonfatal myocardial infarction, or nonfatal stroke).

The primary safety analysis will include all first events that accrue over the pair of PRO2TECT studies. The sample size for the MACE endpoint is based on a 2-sided 95% confidence interval for the hazard ratio (HR) (vadadustat/darbepoetin alfa) and a noninferiority margin of 1.25 (upper bound of the 95% confidence interval) for FDA decision making. Under the assumption that the MACE rate is the same in the 2 groups (i.e., the HR =1), 631 subjects with MACEs will be required in the 2 trials combined to have 80% power to establish noninferiority. If the HR is 0.95 favoring vadadustat, the power will be above 90%. Based on a noninferiority margin of 1.30 for EMA decision making, the power will be above 90% under the assumption that the HR is 1.

Additional safety presentations are described below ([Section 7](#) and [Section 10](#)).

## 3 ANALYSIS POPULATIONS

### 3.1 The Analysis Populations

Each study has the following four analysis populations:

- Randomized population: all subjects randomized. Analyses of this population will be based on the randomized treatment.
- Full Analysis Set (FAS) population: all subjects in the randomized population who received at least 1 dose of study medication and had at least 1 post dose Hb . Analyses of this population will be based on the randomized treatment.
- Safety population: all subjects in the randomized population who received at least 1 dose of study treatment. Analysis of this population will be based on the actual treatment received. Subjects who received in error some vadadustat and some darbepoetin alfa (excluding rescue therapy) will be classified by the more frequently received drug.
- Per Protocol (PP) population: all randomized subjects who received study medication during the PEP, had at least 1 Hb assessments during the PEP, and had no critical or major protocol deviation affecting the primary endpoint analyses, i.e., prior to Week 36. Analyses of this population will be based on actual treatment received, as described for the Safety population.

Major protocol deviations or causes for site closure leading to exclusion from the PP populations will be specified prior to database lock on a blinded basis.

Efficacy analyses will utilize the randomized, FAS, and PP populations while safety analyses (including analyses of MACE) will utilize the safety population.

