11.2 Study Analysis Populations

The following analysis populations will be used in this study:

- Randomized population: defined as all randomized subjects
- Full analysis population: defined as randomized subjects receiving 1 or more doses of study medication and had at least one Hb assessment during the primary efficacy evaluation period. This population will be analyzed based upon the randomized treatment.
- Per protocol (PP) population: defined as all randomized subjects who received study medication (vadadustat or darbepoetin alfa) during the primary evaluation period, had at least 2 Hb assessments during the primary evaluation period, received no rescue therapy (with ESA or RBC transfusion) in the 8 weeks prior to the evaluation period, and have no protocol deviations affecting the primary endpoint analyses. Protocol deviations leading to exclusion from the per protocol population will be specified prior to database lock on a blinded basis and recorded in a separate document.
- Safety population: defined as all subjects who received at least 1 dose of study medication. This population will be analyzed based upon the actual treatment received.

Efficacy analyses will utilize the randomized, full analysis, and PP populations while safety analyses (including MACE) will utilize the randomized population.

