## 1 INTRODUCTION

This statistical analysis plan (SAP) covers the two PRO2TECT studies, Protocols AKB-6548-CI-0014 and AKB-6548-CI-0015, hereafter referred to as CI-0014 and CI-0015, respectively.

The SAP supports the Statistical Methods Section of the clinical study reports (CSRs). It elaborates upon the protocol-specified endpoint definitions and the formal statistical methods that will be used in analyzing both studies. Unless otherwise specified, all analyses will be conducted for each study separately.

Throughout this SAP, planned analyses of both studies are identical to each other except in those places that specifically identify where the plans diverge. Akebia does not intend to pool data together for formal efficacy and general safety analyses; however, analyses of major adverse cardiovascular events (MACE) will be pooled from both studies. A separate SAP will describe the planned methodology for the MACE analyses.

If the analyses described in the protocols differ from those in this SAP, the methods of the SAP prevail.

This SAP contains language and programming code that specifies the exact intent of each analysis. The sponsor will finalize and sign this document prior to locking the database and unblinding (see [Section 2.5](#)). Many of the analyses described in this SAP are quite complex. A blinded team of clinicians and statisticians will review the data carefully to develop conventions and analytic methods not anticipated in writing this SAP.

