#### 9.1.2 Hb in the Primary Efficacy Period

Hb for the PEP will be calculated as the average of all Hb measurements from the central laboratory within the four visit windows during Weeks 24 through 36, regardless of intercurrent events. At least 1 Hb measurement is required for the calculation; otherwise, the value will be missing and therefore imputed. The PEP corresponds to Visits 10 through 13, also called analysis time period 3 ([Table 1](#)).

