### 9.1.5 Sensitivity Analyses to the Primary Efficacy Results

To assess the robustness of the findings from the primary analysis, the following set of sensitivity analyses will be performed using a method analogous to that of the primary analysis (including multiple imputation) unless otherwise specified:

- The primary analysis will be repeated after setting to missing all per-visit Hb values within four weeks of administration rescue therapy or after EOT visits. The definition of rescue therapy will vary across the series described in [Section 6.3.9](#).
- Tipping point analyses (see [Appendix Section B.3.2](#)) will be performed to assess the effect of the missing data.

Statistical Analysis Plan AKB-6548-CI-0014 and AKB-6548-CI-0015

- The FAS population will be used instead of the randomized population without a new multiple imputation. This analysis will be performed only if the size of the FAS is less than 95% of the randomized population.
- The PP population with the actual treatment received without imputation
- A mixed model for repeated measures (MMRM) will be fit to the observed data only *without imputing missing values*. The repeated measures will be the observed averages for analysis time periods 1, 2, and 3 (See definitions in [Section 5.1](#) and analysis details in [Appendix C](#)).

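### The SAP's Per Protocol set omits the protocol's rescue exclusion, so haemoglobin affected by ESA or transfusion can enter that sensitivity analysis

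*SAP*

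**What the plan says.** **Protocol 11.2 (Amendment 7-COL).** A PP subject must have taken study medication in the evaluation period. The Hb requirement is that the subject "had at least 2 Hb assessments during the primary evaluation period". The rescue condition, stated next, is that the subject "received no rescue therapy (with ESA or RBC transfusion) in the 8 weeks prior to the evaluation period". Deviations that affect the primary endpoint also exclude.

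**SAP 3.1.** The PP set is "all randomized subjects who received study medication during the PEP, had at least 1 Hb assessments during the PEP". The remaining condition concerns deviations: the subject "had no critical or major protocol deviation affecting the primary endpoint analyses, i.e., prior to Week 36". It contains no rescue criterion. Arm is assigned by actual treatment as in the Safety population, where subjects given both drugs in error ("excluding rescue therapy) will be classified by the more frequently received drug") are classified without regard to rescue.

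**Precedence.** SAP 1: "If the analyses described in the protocols differ from those in this SAP, the methods of the SAP prevail".

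**Use of the set.** SAP 9.1.5 lists "The PP population with the actual treatment received without imputation" among the sensitivity analyses of the primary result. SAP 9.1.2 builds the PEP value from all central-laboratory Hb in Weeks 24 to 36 "regardless of intercurrent events". The PP bullet adds no rescue or post-treatment rule of its own.

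**The concern.** The primary analysis follows a treatment-policy estimand (SAP 9.1.4), so ESA or transfusion given to vadadustat subjects counts towards the vadadustat mean. In a noninferiority comparison against an ESA, that can bring the arms together and favour the claim. A PP analysis is one place to see whether the result survives without that help.

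Under the SAP wording, a subject rescued in the weeks before the PEP or during it stays in the PP set if some study drug was taken in the PEP and one Hb value exists. Protocol 8.4.7.1 expects study drug to resume after rescue, so many rescued subjects would meet that condition. The PP result could then agree with the primary result partly because both contain the same rescue-affected Hb. The SAP gives no reason for the change from the protocol.

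**Working it through.** **1. The two definitions side by side**

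| Criterion | Protocol 11.2 | SAP 3.1 |
|---|---|---|
| Study drug in the PEP | Any amount | Any amount |
| Hb values in the PEP | At least 2 | At least 1 |
| Rescue in the 8 weeks before the PEP | Excluded | Not mentioned |
| Rescue during the PEP | Not mentioned | Not mentioned |
| Deviations | Those affecting the primary endpoint | Critical or major, before Week 36 |

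The SAP's own changes are the second and third rows and a narrower deviation clause. The lack of minimum exposure and the silence on rescue during the PEP are common to both documents.

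**2. Does another clause remove rescued subjects?**

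- *Deviation clause.* Protocol 8.4.7.1 permits ESA rescue, including at investigator discretion outside the listed criteria, and 8.4.7.2 permits transfusion. Permitted rescue is not in itself a deviation. Inadvertent ESA during vadadustat treatment is one (Protocol 8.5.2) and might be excluded if graded major.
- *Rescue sensitivity analyses (SAP 9.1.5, definitions in 6.3.9).* These blank Hb within four weeks of rescue or after end of treatment (EOT) and rerun the primary model. They cover much of the concern, but differ from a clean PP set in three ways. The window is 4 weeks against the protocol's 8. Missing values are imputed within arm under missing at random (Appendices B.3.1 and B.3.2). Appendix C.1.2 describes the same analysis without the post-EOT condition, while both rescue definitions leave out therapy started after permanent discontinuation.
- *MMRM (SAP 9.1.5, Appendix C.2).* It uses observed data without imputation and has no rescue handling.

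**3. The plan's own power figure**

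Inputs from SAP 2.7: margin −0.75 g/dL, SD 1.5 g/dL, 925 per arm, true difference 0, two-sided 95% interval.

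- SE = 1.5 × √(2/925) = 0.0697.
- Power = Φ(0.75/0.0697 − 1.96) = Φ(8.79) ≈ 1.000, consistent with the stated figure above 90%.
- Size needed for 90%: 2 × (1.96 + 1.2816)² × (1.5/0.75)² = 84.1, so 85 per arm.

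Precision is not the constraint on the PP set; the issue is bias.

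**4. Illustration of the bias**

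Let *f* be the share of vadadustat PP subjects with rescue-affected Hb and *d* the resulting lift in their PEP average. Take the true on-drug difference as exactly −0.75 and assume no rescue effect in the darbepoetin arm.

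- Bias = *f* × *d*.
- P(lower limit above −0.75) = Φ(*f d*/SE − 1.96).

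Two lifts are shown. A lift of 0.5 g/dL is the gap between the protocol's ESA rescue trigger (below 9.0) and its stopping level (9.5 or above). A lift of 0.75 g/dL is full recovery of the assumed deficit. The PP size of 700 per arm is an assumption (SE 0.0802).

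| *f* | *d* = 0.5, n = 925 | *d* = 0.5, n = 700 | *d* = 0.75, n = 925 | *d* = 0.75, n = 700 |
|---|---|---|---|---|
| 0% | 2.5% | 2.5% | 2.5% | 2.5% |
| 2% | 3.5% | 3.3% | 4.0% | 3.8% |
| 5% | 5.5% | 5.0% | 7.7% | 6.8% |
| 10% | 10.7% | 9.1% | 18.8% | 15.3% |
| 20% | 29.9% | 23.8% | 57.6% | 46.4% |

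Example: *f* = 10%, *d* = 0.5, n = 925 gives bias 0.05 and Φ(0.05/0.0697 − 1.96) = Φ(−1.24) = 10.7%. The probability does not scale in proportion to the lift. At n = 700 and *f* = 20%, halving a 0.75 lift takes it from 46.4% to 15.3%, because the bias is then the same 0.075 as at *f* = 10%.

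**The case against.** The case for leaving the SAP alone has real weight.

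- **The question is examined elsewhere.** The narrow and broad-on-treatment analyses have their own seeds (Listing B 1). They reach rescue during the PEP and, as worded in 9.1.5, Hb after EOT, which the protocol's PP rule does not. This stands, and it lowers the importance of the point. It does not make the PP set redundant, for the three reasons in step 2 of the working.
- **Switching.** A reader might infer that someone who takes one tablet in Week 24, stops and returns to an ESA contributes a full PEP of ESA-driven Hb. The documents do not support that as a typical case. SAP 2.2 says no laboratory assessments are planned after permanent discontinuation. The EOT visit includes a blood count (Protocol 9.3.9) and the 4-week follow-up visit does not (9.3.10). Protocol 11.5 does expect visits to continue, so some later values may exist.
- **Exposure wording.** A reader might also infer that the SAP loosened the exposure requirement. It did not; the protocol sets no minimum either.
- **Rescue in the control arm.** Both arms may be rescued. The net bias is the difference between the two arms' contributions, so the table overstates it if darbepoetin subjects are rescued too.
- **The remedy is not neutral.** ESA rescue is tied to low Hb, so excluding rescued subjects selects on a post-randomization event and may remove poor responders. Darbepoetin increases count as rescue only if the investigator designates them so (SAP 6.3.9), so removal may be unequal and could itself favour vadadustat. This stands and must accompany any fix.
- **The deviation log is not in the documents.** Exclusions are to be fixed blind before lock and may catch some of these subjects. Permitted rescue would not fall under the clause without a further rule.

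**Conclusion.** The discrepancy is established by the text. The governing SAP omits a rescue exclusion that the protocol pre-specified, halves the required number of PEP Hb values, and leaves rescue-affected Hb in the PP sensitivity analysis. The protocol's rule is itself incomplete, because it stops at the start of the PEP.

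The consequence is limited. The primary analysis is untouched, no decision rule is attached to the PP result, and the rescue analyses in 9.1.5 address part of the same question. A reader might infer that the noninferiority conclusion goes unchecked for rescue; those analyses show otherwise.

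The size cannot be determined, because the documents give no rescue rates. The table rests on assumed fractions, a true deficit exactly at the margin and rescue effects in one arm only. Its 10% to 20% rows with full recovery are an upper illustration, not an estimate: rescue stops at Hb 9.5, below the 10.0 floor of the target range, and study drug then resumes. With a lift of 0.5 g/dL in 2% to 10% of vadadustat PP subjects, the chance of wrongly passing at 925 per arm is 3.5% to 10.7%, against a nominal 2.5%.

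The change should be made, as a correction to a sensitivity analysis.

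**What to change.** 1. In SAP 3.1, restore the protocol's rescue exclusion and extend it through the PEP: exclude subjects meeting the broad-on-treatment definition (6.3.9) in the 8 weeks before or during the PEP. State the anchor day. Eight weeks (56 days) before the SAP window opens on Study Day 155 is Day 99; before the Week 24 target of Day 168 it is Day 112.
2. For the PP analysis, average only PEP Hb values taken up to the last study dose.
3. Restore the two-value requirement or give a reason for one.
4. Reconcile Appendix C.1.2 with 9.1.5 so that both state whether post-EOT Hb is set to missing.
5. Report the number excluded from the PP set for rescue by arm, and read the PP result alongside the rescue analyses in 9.1.5.

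The cost is SAP wording and programming of one analysis set before lock. The PP set shrinks and its interval widens, which matters little given that 85 per arm would already give 90% power. The real cost is the post-randomization selection described above, which item 5 makes visible but does not remove. The primary analysis and all stated power figures stay as they are.

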### 3.2 Characterization of the Analysis Population

Number and percent of subjects included in the analysis sets will be summarized.

## 4 QUALITY OF THE TRIALS

### 4.1 Study Drug Dosing and Compliance

Subjects track their own drug use at home. At each visit, the site records each subject's self-reported compliance.

The proportion of subjects who report at least 80% compliance at each visit will be tabulated and summarized for both safety population and FAS.

In addition to self-reported compliance, the calculated compliance rate for a given time period will be derived from exposure data as the number of days on dosing period collected on electronic case report forms (eCRFs) divided by the number of days in that time period.

### 4.2 Protocol Deviations

Definitions of critical, major, and minor protocol deviations will be described in master Protocol Deviation log file, including those protocol deviations leading to exclusion from the PP populations. These will be specified prior to database lock on a blinded basis.

Protocol deviations will be summarized in the randomized population as the number and percentage of subjects with a protocol deviation by treatment group and study period. A by-subject listing of protocol deviations, indicating those exclusionary from the PP population, will be provided.

### 4.3 Baseline Characteristics, Exposure, and Retention by Treatment Group

Baseline characteristics collected in the case report form (CRF) will be summarized in analysis populations ([Section 3](#)). Summaries of demographics, medical history, prior and concomitant medications, and treatment exposure will be displayed by treatment groups.

The total number of randomized subjects by treatment group and the number randomized but not treated will be tabulated. This summary will be performed in the randomized population.

The average weekly dosages by treatment groups will be categorized for the safety and FAS populations(see [Section 5.1](#)).

The number of subjects who discontinued treatment and the reason for treatment discontinuation will be tabulatedfor the Randomized populations.

## 5 GENERAL CONVENTIONS

Study days are defined as follows:

$$\text{Study Day} = \begin{cases} [\text{Event date} - \text{First dosing date} + 1] & \text{if after first dosing date} \\ [\text{Event date} - \text{First dosing date}] & \text{if before first dosing date.} \end{cases}$$

Note that with the definition above, days of "0" will not be used. As such, the study day can be interpreted as the number of days before or after first day of dosing. Event date refers to the date associated with the result being summarized. In some cases, this is the date of an assessment or measurement; in other cases, this is the onset date of an adverse or outcome event.

For subjects whose reference date is missing, the study day will also be categorized as missing.

